4.3 Recruitment

Healthy control subjects will be recruited via clinical research sites and clinically assessed for the "absence" of painful and/or swollen joints. RA subjects will be recruited from rheumatology practices in accordance with the inclusion and exclusion criteria listed above. Candidate subjects will be asked by their treating physician about their willingness to participate in the study.

4.4 Withdrawal

In accordance with the Declaration of Helsinki, each subject is free to withdraw from the study at any time and without providing a reason.

A subject who withdraws consent prior to receiving Tc 99m tilmanocept injection on Day 0 will be considered a screen failure.

Should a subject withdraw after administration of the investigational product, all efforts will be made to complete and report the observations up to the time of withdrawal as thoroughly as possible. An explanation should be given of why the subject is withdrawing or being withdrawn from the study.

The investigator may withdraw a subject from the study at any time at the discretion of the investigator for any of the following reasons:

- A protocol violation occurs
- A serious or intolerable AE occurs
- A clinically significant change in a laboratory parameter occurs
- At the investigator's/sponsor's discretion as long as it is in the best interest of the subject
- The sponsor or investigator terminates the study
- The subject requests to be discontinued from the study

4.5 Replacement

Subjects will be replaced if they have not completed all study procedures necessary for the primary endpoint(s) relevant to their study arm or their data are determined to be not evaluable. A subject is considered evaluable if he/she meets the criteria for the analysis population and has the data necessary for computing the primary endpoint.

4.6 Screen Failures

Subjects who sign an informed consent form (ICF) but are ultimately not injected will be considered a screen failure. Subjects will be assigned a study identification number at the time the ICF is signed. eCRFs for Informed Consent, Inclusion, Exclusion, Demographics, Adverse Events, and final disposition should be completed for all screen failure subjects.

4.7 Subject Identification

After the subject provides written informed consent, the site will assign the subject a 7-digit subject number. Subject numbers are to be assigned in a sequential manner using the following format:

Digits 1 to 2: Study number "35"

Digits 3 to 4: Site number (e.g., "01")

Digits 5 to 7: Sequential subject number (e.g., "001", "002", "003") For example, the first subject consented at Site 01 is subject number "35-01-001."

Subjects will maintain the same number given at screening for the entire study. If a subject is a screen failure, the number will not be used for any other subject.
5 INVESTIGATIONAL PRODUCT

5.1 Description of Investigational Project

Technetium Tc 99m tilmanocept is a scintigraphic imaging radiotracer that binds to CD206 (mannose-binding receptor) on the surface of macrophages and other inflammatory cells. It is comprised of multiple units of DTPA (diethylenetriaminepentaacetic acid) and mannose, each synthetically attached to a 10 kDa dextran backbone (Figure 1). The mannose acts as a substrate for the receptor and the DTPA serves as a chelating agent for labeling with Tc 99m. Tilmanocept has a diameter of about 7 nm, which permits enhanced diffusion into lymph nodes and blood capillaries.

<section-header>

Figure 1 Tc 99m tilmanocept and the Mannose Receptor

5.2 Investigational Product Dosage and Administration

Tc 99m tilmanocept will be administered through an IV route of injection. A 150-mcg dose containing 10 mCi of Tc 99m in 3 mL will be delivered using 1 syringe. The dose will be injected as a slow push into the IV catheter. At the completion of the injection, a 10-mL sterile normal saline flush will be administered. The preferred site of IV placement will be between the left or right antecubital vein.

The final administered dose will be \pm 20% of the tilmanocept mass dose and radiolabel mCi dose.

5.3 Timing and Frequency of Drug Administration

Subjects in either arm will receive the study-defined dose of 150 mcg tilmanocept radiolabeled with 10 mCi of Tc 99m on Day 0 Visit 2.

5.4 Packaging and Labeling

Tilmanocept cartons ready for radiolabeling will be shipped and stored at the study-assigned radiopharmacy. Tilmanocept is provided in a vial. Vials are packaged as a kit. A carton (kit) contains 5 vials of tilmanocept.

A detailed Radiolabeling protocol will be provided to each radiopharmacy for instructions on how to radiolabel the vials and prepare the final tilmanocept product for injection. Quality Control worksheets will also be provided.

5.5 Drug Logistics and Investigational Product Accountability

The investigator (or designated personnel) will confirm receipt of the investigational product in writing and will use the investigational product only within the framework of this clinical study and in accordance with this study protocol. For each subject, he/she will keep a record of the investigational product dispensed and store all other forms that accompanied the delivery of the radiolabeled product to the clinical site. These documents are to be filed in the investigator site file. Overall drug accountability and reconciliation will be completed by the sponsor or its representative. A list of investigational product vials and other materials that were returned, or destroyed, must be recorded and signed by the PI or an appropriately qualified designee as documented in the study site responsibility sheet. An overall accountability and reconciliation form of the investigational product will be prepared and completed. If there are any discrepancies, they must be investigated and their resolution documented. All unused study kits will be destroyed in accordance with institutional destruction procedures.

6 THERAPIES OTHER THAN INVESTIGATIONAL PRODUCT

6.1 **Prior and Concomitant Therapies**

All medications taken 30 days prior to Tc 99m tilmanocept injection through the post-injection safety follow-up must be documented and maintained at a stable dose according to the inclusion criteria. Subjects receiving radiation therapy or chemotherapy are not eligible for participation in the trial. If applicable, the subject's history of RA treatments for up to 6 months will also be collected.

6.2 Post-Study Therapy

There are no post-study therapy restrictions.

7 STUDY PROCEDURES

A schedule of evaluations is provided in the schedule of events (Appendix 1).

7.1 Schedule of Evaluations

7.1.1 Arm 1

Visit 1 (Screening; Day -30 to Day -1)

- Preliminary review of inclusion and exclusion criteria
- Obtain signed informed consent for study participation
- Allocation of unique subject number; this number will be used to document the subject data in the case report forms (CRFs) and enrollment log
- Demography date of birth, gender, race, ethnicity
- Medical surgical history all relevant prior medical and surgical conditions will be recorded in the CRF. Documented medical conditions will also note the month and year of onset if the condition is still active.
- Concomitant medications (within 30 days before injection).
- Vital signs (body temperature, heart rate, blood pressure, and respiratory rate after at least 1 minute in a resting position)
- Physical examination will include an assessment of height, weight, and examination of general appearance, skin, eyes, ears, nose, throat, head and neck (including thyroid), lungs, heart, abdomen, lymph nodes, musculoskeletal, and nervous system. Any clinically relevant finding is to be documented as a baseline finding. Physical exams that are conducted as standard of care prior to signing informed consent may be used if they are performed within 30 days of injection.
- Clinical laboratory tests study subjects will have blood obtained for hematology, chemistry, and an RA panel (see Table 7)
- Urine collection for routine analysis
- Urine pregnancy test for women of child-bearing potential. Females of child bearing potential are defined as women that are not surgically sterile (hysterectomy or bilateral oophorectomy) nor postmenopausal for at least 1 year prior to screening. Women who are not of childbearing potential will not require a pregnancy test.
- 2010 ACR/EULAR: to confirm that the subject is clinically free of inflammatory disease and joint pain Swollen and tender joints will be identified and documented during physical examination as established by the 2010 ACR/EULAR.

Visit 2 (Tc 99m Tilmanocept Administration and Imaging; Day 0)

All subjects will be assessed for adverse events in an ongoing manner from the day of injection through the end of participation.

Pre-Tc 99m Tilmanocept Administration

The following procedures will be completed for all subjects on the day of injection prior to the administration of Tc 99m tilmanocept:

- A urine pregnancy test for women of child-bearing potential. Females of child bearing potential are defined as women that are not surgically sterile (hysterectomy or bilateral oophorectomy) nor postmenopausal for at least 1 year prior to screening. Women who are not of childbearing potential will not require a pregnancy test.
- Assessment of adverse events
- Concomitant medication review
- Vital signs after at least 1 minute in a resting position (body temperature, heart rate, blood pressure, and respiratory rate) within 30 minutes prior to administration of Tc 99m tilmanocept

Tc 99m Tilmanocept Administration

IV administration of Tc 99m tilmanocept will be at study time 00:00. The preferred site of IV placement will be the left or right antecubital vein. The filled syringe will be connected to the catheter for a slow push injection (30-60 seconds). At the completion of the injection, a 10-mL sterile normal saline flush will be administered. The IV administration will be performed in the nuclear medicine department by an onsite Certified Nuclear Medicine Technologist or Nuclear Medicine Physician. Subjects will be continuously monitored for adverse events.

0-30 Minutes Post-Tc 99m Tilmanocept Administration

- Assessment of adverse events
- Vital signs after at least 1 minute in a resting position (body temperature, heart rate, blood pressure, and respiratory rate)

60 - 75 Minutes Post-Tc 99m Tilmanocept Administration

- Assessment of adverse events
- Image acquisition: Planar scan of the bilateral hands and wrists acquired per NAV3-35 Image Acquisition Guidelines

Visit 3 (Day 5 ± 3; Follow-up Telephone Safety Assessment)

- Review of concomitant medications
- Assessment of adverse events

7.1.2 Arm 2

Visit 1 (Screening; Day -30 to Day -1)

- Preliminary review of inclusion and exclusion criteria
- Obtain signed informed consent for study participation
- Allocation of unique subject number; this number will be used to document the subject data in the case report forms (CRFs) and enrollment log
- Demography date of birth, gender, race, ethnicity
- Medical surgical history all relevant prior medical and surgical conditions will be recorded in the CRF. Documented medical conditions will also note the month and year of onset if the condition is still active.
- Concomitant medications (within 30 days before injection).
- Vital signs (body temperature, heart rate, blood pressure, and respiratory rate after at least 1 minute in a resting position)
- Physical examination will include an assessment of height, weight, and an examination of general appearance, skin, eyes, ears, nose, throat, head and neck (including thyroid), lungs, heart, abdomen, lymph nodes, musculoskeletal, and nervous system. Any clinically relevant finding is to be documented as a baseline finding. Physical exams that are conducted as standard of care prior to signing informed consent may be used if they are performed within 30 days of injection.
- Clinical laboratory tests study subjects will have blood obtained for hematology, chemistry, and an RA panel (Section 8.8)
- Urine collection for routine analysis
- Urine pregnancy test for women of child-bearing potential. Females of child bearing potential are defined as women that are not surgically sterile (hysterectomy or bilateral oophorectomy) nor postmenopausal for at least 1 year prior to screening. Women who are not of childbearing potential will not require a pregnancy test.
- RA Evaluations: Swollen and tender joints will be identified and documented during physical examination as established by the 2010 ACR/EULAR for both HCs and RA subjects. RA subjects will also undergo a DAS28 evaluation and a review of RA history including previous treatments, date of symptom onset, and date of diagnosis.

Visit 2 (Day 0; Tc 99m Tilmanocept Administration and Imaging)

All subjects will be assessed for adverse events in an ongoing manner from the day of injection through the end of participation.

Pre-Tc 99m Tilmanocept Administration

The following procedures will be completed for all subjects on the day of injection prior to the administration of Tc 99m tilmanocept:

• A urine pregnancy test for women of child-bearing potential. Females of child bearing potential are defined as women that are not surgically sterile (hysterectomy or bilateral

oophorectomy) nor postmenopausal for at least 1 year prior to screening. Women who are not of childbearing potential will not require a pregnancy test.

- Assessment of adverse events
- Concomitant medication review
- Vital signs after at least 1 minute in a resting position (body temperature, heart rate, blood pressure, and respiratory rate) within 30 minutes prior to administration of Tc 99m tilmanocept

Tc 99m Tilmanocept Administration

IV administration of Tc 99m tilmanocept will be at study time 00:00. The preferred site of IV placement will be the left or right antecubital vein. The filled syringe will be connected to the catheter for a slow push injection (30-60 seconds). At the completion of the injection, a 10-mL sterile normal saline flush will be administered. The IV administration will be performed in the nuclear medicine department by an onsite Certified Nuclear Medicine Technologist or Nuclear Medicine Physician. Subjects will be continuously monitored for adverse events.

0 to 30 Minutes Post-Tc 99m Tilmanocept Administration

- Assessment of adverse events
- Vital signs after at least 1 minute in a resting position (body temperature, heart rate, blood pressure, and respiratory rate)

60 - 75 Minutes Post-Tc 99m Tilmanocept Administration

- Assessment of adverse events
- Image acquisition (in the following order):
 - 1. Planar scan of the bilateral hands and wrists acquired per NAV3-35 Image Acquisition Guidelines followed by preparation (up to 10 minutes) for the subsequent scan;
 - 2. SPECT/CT of the bilateral hands and wrists acquired per NAV3-35 Image Acquisition Guidelines

Visit 3 (Day 5 ± 3; Follow-up Telephone Safety Assessment)

- Review of concomitant medications
- Assessment of adverse events

8 PROCEDURES AND VARIABLES

8.1 **Population Characteristics**

8.1.1 Demographics and Other Baseline Characteristics

One-hundred and thirty-five (135) evaluable subjects will be enrolled across the 2 study arms. Arm 1 will be comprised of 120 male or female HC subjects who are clinically free of any inflammatory and/or joint disease. Arm 2 will be comprised of 15 subjects. Ten (10) subjects in Arm 2 will be male or female individuals with clinically diagnosed active RA who are on stable anti-inflammatory and/or anti-rheumatic therapy. Five (5) subjects in Arm 2 will be male or female HCs who are clinically free of any inflammatory and/or joint disease. Enrolled HCs in either Arm will be categorized by age and sex to ensure intended distributions are met for the normative database, as described in Section 9.4.

8.1.2 Medical, Rheumatological, and Surgical History

Relevant medical, rheumatological, and surgical histories will be obtained on all study subjects. As part of the medical history, the date of the last spontaneous menstruation will be recorded if childbearing potential is not excluded by surgical sterilization. Rheumatological history will include date of RA diagnosis as well as the timing, dose, administration frequency, and administration route (when available) of all RA-specific drugs taken in the last 6 months.

8.1.3 Prior and Concomitant Medication

All prior non-RA medications used up to 30 days before the first screening examination through the follow-up safety visit will be documented. In addition to the summarization of prior RA-specific treatments, recent or concomitant treatments taken for RA in the last 6 months must be collected.

8.2 Tc 99m Tilmanocept Administration

Tc 99m tilmanocept must be ordered from the study-assigned radiopharmacy once the subject has been scheduled for IV administration and imaging. The preferred site of IV placement will be the left or right antecubital vein. The filled syringe will be connected to the catheter for a slow push injection. Immediately after the completion of the injection, a 10-mL sterile normal saline flush will be administered. Injection of Tc 99m tilmanocept will be at study time 0:00.

8.3 Rheumatological Assessments

8.3.1 2010 ACR/EULAR Classification Criteria

All subjects will be evaluated at screening using the 2010 ACR/EULAR Classification Criteria as part of eligibility and inclusion (Aletaha et. al 2010). The 2010 ACR/EULAR classification criteria includes 4 components: number and site of involved joints, serologic abnormality, elevated acute-phase response and symptom duration. See Appendix 5 for details. A total score

of 6 or higher (out of a possible 10) combined with clinical synovitis not better explained by another disease confirms a diagnosis of "definite RA".

8.3.2 DAS28

RA subjects in Arm 2 will receive the DAS28 evaluation (Prevoo et. al 1995) at screening as part of eligibility and inclusion. DAS28 is calculated from 4 components: tender joint count (TJC), swollen joint count (SJC), visual analogue scale (VAS) of the subject's global health, and the laboratory parameter erythrocyte sedimentation rate (ESR), such that:

$$DAS28 = 0.56\sqrt{TJC} + 0.28\sqrt{SJC} + 0.7\ln(ESR) + 0.014(VAS)$$

A DAS28 score of higher than 5.1 is indicative of high disease activity whereas a DAS28 below 3.2 indicates low disease activity. A subject with a DAS28 lower than 2.6 is considered to be in remission. For consistent scoring, the following calculator should be utilized: https://qxmd.com/calculate/. See Appendix 3 for details.

8.3.3 Other

8.3.3.1 28-joint Count (SJC and TJC)

The 28-joint count will be performed for swollen and/or tender joints in the following: shoulder, elbow, wrist, MCP and PIP, and knee. Joint swelling is defined as soft tissue swelling that is detectable along the joint margins. Joint tenderness is defined as the presence of pain in a joint at rest with pressure or on movement of the joint [57]. This assessment will be used as an input parameter for 2010 ACR/EULAR score and DAS28 score.

8.3.3.2 Patient Assessment of Pain (VAS)

Patient assessment of pain will be evaluated using the visual analog scale (VAS). Using a ruler, the score will be determined by measuring the distance (mm) on the 10-cm line between the 'no pain' anchor and the patient's mark, providing a range of scores from 0 to 100. This assessment will be used as an input parameter for DAS28 score.

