- 5. The subject is not currently on anti-inflammatory drugs (including non-steroidal anti-inflammatory drugs [NSAIDs]) and has not taken any anti-inflammatories for at least 28 days prior to the consent date.
- 6. For all ongoing concomitant medications, the subject has maintained a stable dose for at least 28 days prior to the consent date.

RA SUBJECTS

- 3. The subject is at least 18 years of age and was ≥ 18 years of age at the time of RA diagnosis.
- The subject has moderate to severe RA as determined by the 2010 American College of Rheumatology/European League Against Rheumatism (ACR/EULAR) Classification Criteria (score of ≥ 6/10).
- 5. The subject has a 28-joint disease activity score (DAS28) of ≥ 3.2 (includes the Erythrocyte Sedimentation Rate [ESR] test and Visual Analog Scale [VAS]).
- 6. Subjects receiving traditional DMARDs must have been on therapy for ≥ 90 days and at a stable dose for ≥ 30 days prior to the imaging visit (Day 0).
- 7. If the subject is receiving bDMARD or janus kinase (JAK) inhibitor therapy, they have been at a stable dose > 60 days prior to the imaging visit (Day 0).
- If the subject is receiving NSAIDs or oral corticosteroids, the dose has been stable for ≥ 28 days prior to the imaging visit (Day 0). The corticosteroid dose must be ≤ 10 mg/day of prednisone or an equivalent steroid dose.

Exclusion Criteria:

- 1. The subject is pregnant or lactating.
- 2. The subject size or weight is not compatible with imaging per the investigator.
- 3. The subject is currently receiving radiation therapy or chemotherapy or has received radiation therapy or chemotherapy in the past six months.
- 4. The subject has had a finger, hand, and/or wrist amputation or hand or wrist joint arthroplasty.
- 5. The subject has renal insufficiency as demonstrated by a glomerular filtration rate of < 60 mL/min.

- 6. The subject has hepatic insufficiency as demonstrated by ALT (alanine aminotransferase [SGPT]) or AST (aspartate aminotransferase [SGOT]) greater than 2 times the upper limit of normal.
- 7. The subject has any severe, acute, or chronic medical conditions and/or psychiatric conditions and/or laboratory abnormalities that would impart, in the judgment of the investigator, excess risk associated with study participation or study drug administration that would deem the subject inappropriate for study participation or compromise the safety of the subject or the quality of the data.

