4.2.1 Inclusion Criteria

ALL SUBJECTS

- 1. The subject has provided written informed consent with HIPAA authorization before the initiation of any study-related procedures.
- 2. The subject has agreed to not engage in any diet, lifestyle, or medication changes until study completion.

HEALTHY CONTROL SUBJECTS

- 3. The subject is 30 years of age or greater at the time of consent.
- 4. The subject is deemed to be clinically free of any inflammatory disease(s), autoimmune disease(s), or arthropathies and has not experienced joint pain for at least 28 days prior to the consent date.

- 5. The subject is not currently on anti-inflammatory drugs (including NSAIDs) and has not taken any anti-inflammatories for at least 28 days prior to the consent date.
- 6. For all ongoing concomitant medications, the subject has maintained a stable dose for at least 28 days prior to the consent date.

CLINICALLY DIAGNOSED ACTIVE RA SUBJECTS

- 3. The subject is at least 18 years of age and was ≥ 18 years of age at the time of RA diagnosis.
- 4. The subject has moderate to severe RA as determined by the 2010 ACR/EULAR Classification Criteria (score of $\geq 6/10$).
- 5. The subject has a DAS28 of \geq 3.2 (includes the ESR test and VAS).
- 6. If the subject is receiving traditional DMARDs, they have been on therapy for ≥ 90 days and at a stable dose for ≥ 30 days prior to the imaging visit (Day 0).
- 7. If the subject is receiving bDMARD or JAK inhibitor therapy, they have been at a stable dose > 60 days prior to the imaging visit (Day 0).
- 8. If the subject is receiving NSAIDs or oral corticosteroids, the dose has been stable for ≥ 28 days prior to the imaging visit (Day 0). The corticosteroid dose must be ≤ 10 mg/day of prednisone or an equivalent steroid dose.

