Appendix 3 DAS28 Scoring

- 3. Obtain and record the patient's general health on a Visual Analog Scale (VAS) of 100 mm in the appropriate box on Form B. Note: DAS28 calculations may be performed without a VAS measurement.
- 4. Plug the appropriate values into the formula at the bottom of Form B (many online calculators are available to compute this value including http://www.das-score.nl/www.das-score.nl/dasculators.html).
- 5. A DAS28 score of higher than 5.1 is indicative of high disease activity, whereas a DAS28 below 3.2 indicates low disease activity. A patient is considered to be in remission if they have a DAS28 lower than 2.6.

Courtesy of http://www.iche.edu/newsletter/DAS28.pdf

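### The protocol defines the DAS28 VAS as global health but describes collecting a pain VAS as the DAS28 input, so the 3.2 entry score for RA subjects could be computed on a variable the definition does not name

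*Protocol*

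**What the plan says.** **Entry criterion.** Protocol 4.2.1, RA criterion 5, sets the DAS28 threshold at "3.2 (includes the ESR test and VAS"). The Synopsis states the same criterion and also says that the score "includes the Erythrocyte Sedimentation Rate [ESR] test and Visual Analog Scale [VAS"]. Neither says what the VAS measures.

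**Definition.** Protocol 8.3.2 states that "DAS28 is calculated from 4 components": tender joint count, swollen joint count, ESR and a "visual analogue scale (VAS) of the subject's global health". It prints the formula, with coefficient 0.014 on the VAS, and names one web calculator for consistency.

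**Measurement.** Protocol 8.3.3.2 is headed as a pain assessment: "Patient assessment of pain will be evaluated using the visual analog scale (VAS"). The score is the distance "between the 'no pain' anchor and the patient's mark, providing a range of scores from 0 to 100". The section closes by making this assessment an input to DAS28. No other body section describes how a VAS is collected.

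**Appendix 3.** The scoring instructions ask for the patient's general health on a 100 mm VAS, then note that "DAS28 calculations may be performed without a VAS measurement". They remark that many online calculators exist and give a different example from the one in 8.3.2.

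**SAP.** The shell of Data Listing 19 (Appendix B) has a patient VAS column labelled global, in mm. SAP 6.4 says DAS28 results will be listed.

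**The concern.** Pain and global health are different questions, and a subject can mark them differently on a 100 mm line. The protocol defines its entry score with one and describes collecting the other for the same slot in the formula. 8.3.2 and 8.3.3.2 both sit in section 8.3 of the current text, so this is not a matter of superseded wording. A site that built its worksheet from 8.3.3.2 and a site that worked from 8.3.2 or Appendix 3 would each be following the protocol, yet they could score the same subject differently against 3.2.

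What is at stake is the consistency of one eligibility score in a study with up to 8 centers. The threshold is one of the criteria by which the RA group of Arm 2 is described as having active disease. There is also a labelling risk: if the pain score is what is collected, the SAP listing would present it under a global heading.

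**Working it through.** The documents state no figure that depends on the choice of VAS, so there is nothing to reproduce. The check sets the passages side by side and then uses the protocol's own formula to see whether the choice can move a subject across 3.2.

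**Which VAS does each place name?**

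| Place | VAS in DAS28 |
|---|---|
| Protocol 8.3.2 | Global health; one of four components |
| Protocol 8.3.3.2 | Pain, measured from a no-pain anchor; stated to be the DAS28 input |
| Protocol Appendix 3 | General health; then a note that it may be omitted |
| SAP Data Listing 19 shell | Global |
| Synopsis and 4.2.1, RA criterion 5 | VAS included; construct not named |

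Three places agree on global or general health. The section that describes the measurement does not.

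**How far can the VAS term move the score?** The formula in 8.3.2 is

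DAS28 = 0.56√TJC + 0.28√SJC + 0.7 ln(ESR) + 0.014 × VAS

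- Range of the VAS term: 0 to 0.014 × 100 = 1.4 points.
- Shift from a gap between the pain and global marks. The gaps are assumptions; the documents give no figure:
  - 10 mm: 0.014 × 10 = 0.14
  - 20 mm: 0.014 × 20 = 0.28
  - 30 mm: 0.014 × 30 = 0.42
  - 40 mm: 0.014 × 40 = 0.56

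**Who can change status?** Only a subject whose two scores fall on opposite sides of 3.2. For a 10 mm gap, the score on the defined VAS must lie within 0.14 of the cutoff, that is between 3.06 and 3.34. For a 40 mm gap it must lie within 0.56, that is between 2.64 and 3.76.

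**Illustrations** (joint counts, ESR and VAS are assumed values):

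- TJC 2, SJC 1, ESR 12. The first three terms give 0.56√2 + 0.28√1 + 0.7 ln 12 = 0.792 + 0.280 + 1.739 = 2.811. Reaching 3.2 needs a VAS of (3.2 − 2.811)/0.014 = 27.8 mm. At 20 mm the score is 3.09 and the subject is not eligible on this criterion; at 40 mm it is 3.37 and the subject is. A 20 mm difference between the two marks decides entry here.
- TJC 4, SJC 2, ESR 15. The first three terms give 1.120 + 0.396 + 1.896 = 3.412. The subject passes with a VAS of zero, so the choice of VAS makes no difference.

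**What else depends on DAS28?** The efficacy variables and endpoints (Protocol 9.3, SAP 4.1) and their analyses (Protocol 9.5.3, SAP 4.2) do not use it. The Arm 1 normal limits come from healthy controls, who have no DAS28. The sample size text (Protocol 9.4, SAP 1.3) does not use it either.

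**The case against.** The strongest case is that this is a wording slip with almost no consequence. DAS28 is used only at screening, and the SAP does no more than list it. Arm 2 is a descriptive feasibility arm with no hypothesis test and no DAS28 subgroup. RA subjects must also score at least 6 of 10 on the 2010 ACR/EULAR criteria, which use no VAS. The listing's global column is equally consistent with a CRF that already collects global health, in which case only the text of 8.3.3.2 is wrong. All of this stands, and it limits the size of the point. It does not remove the conflict between 8.3.2 and 8.3.3.2, because the CRF is not among the documents and 8.3.3.2 is the instruction sites have in front of them.

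A reader might also infer that the protocol offers a third valid way to qualify, namely a DAS28 with no VAS. The documents do not support that. Criterion 5 says the entry score "includes the ESR test and VAS", and 8.3.2 defines four components. The Appendix 3 remark is a general note in reproduced outside material; the available text starts at step 3 and gives no three-component formula. It conflicts with the criterion and should be aligned, but it does not open another route to eligibility.

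Nor do the two calculator references show that sites would obtain different scores from the same inputs. 8.3.2 instructs the use of one; Appendix 3 only mentions that others exist. The formula is printed, and nothing in the documents shows that the calculators differ.

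**Conclusion.** The point holds for the VAS construct. The definition, Appendix 3 and the SAP listing name global or general health, while the measurement section collects pain and sends it into the score. Followed as written, 8.3.3.2 puts into the entry score a variable other than the one the definition names.

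The size is limited. A pain/global gap of 10 to 40 mm, which is an assumed range, shifts DAS28 by 0.14 to 0.56. Ten RA subjects is a ceiling on the number affected: only those near 3.2 could change eligibility, and the documents give no basis for saying how many that would be. It would be wrong to infer that the trial's results are at risk, since no endpoint, normal limit or sample size uses DAS28. The point is worth correcting because the text contradicts itself on an entry criterion and the correction is cheap. Which VAS is clinically appropriate is for the sponsor to settle.

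**What to change.** Reconcile Protocol 8.3.2, 8.3.3.2 and Appendix 3 with SAP Data Listing 19, in one of two ways: either the VAS collected is the one the DAS28 definition names, with matching heading and anchors in 8.3.3.2; or 8.3.3.2 states that the pain VAS is a separate assessment and not a DAS28 input, and the protocol says where the DAS28 VAS is collected.

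In the same edit, align the Appendix 3 note on computing DAS28 without a VAS with RA inclusion criterion 5. As a minor tidy-up, refer to a single calculator in both places.

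The cost is protocol wording and, if the CRF carries the same mismatch, one label. No analysis changes.
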